4.4.1.1 Handling of Missing Data

- All observed assessments will be included in the analyses. No imputation for missing MFM scores will be performed.
- Following the death of a patient, MFM scores will be set to missing.
- If an individual MFM item is missing or was 'Not done,' the item will be set to zero in accordance with the MFM user manual.

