2.2 DETERMINATION OF SAMPLE SIZE

The sample size will be determined by the number of patients who participated in study TRO19622CLEQ1115-1 or TRO19622CLEQ1275-1 (170 in total) who meet the enrollment criteria and who consent to participate in the treatment phase of study BN29854.

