4.4 EFFICACY ANALYSIS

As this is a single arm, open-label study no formal hypothesis testing will be performed. Data collected during the treatment phase of this study will be summarized using descriptive statistics and will be compared with observational data describing the natural history of the disease.

The baseline value will be defined as the last non-missing value recorded prior to or on the first day of the study drug (Study Day 1).

Post-baseline efficacy assessments (scheduled every 26 weeks), including assessments performed at an early discontinuation visit, will be assigned to a scheduled study visit based on the following time windows:

Visit	Study Day	Time Window (in Study Days)
V3 (Week 26)	183	Day 2 – Day 274
V5 (Week 52)	365	Day 275 – Day 456
V6 (Week 78)	547	Day 457 – Day 638
V7 (Week 104)	729	Day 639 – Day 820
V8 (Week 130)	911	Day 821 – Day 1002
V9 (Week 156)	1093	Day 1003 – Day 1184
V10 (Week 182)	1275	Day 1185 – Day 1366
V11 (Week 208)	1457	Day 1367 – Day 1548
...		

If multiple valid values for a variable are recorded in the same time window, the record closest to the scheduled study visit will be selected for summary of the data.

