4.4.1 Primary Efficacy Endpoint

The primary efficacy outcome measure is the MFM D1+D2 score. MFM-32 is expected to be performed by all patients throughout study BN29854. If a patient erroneously performs the MFM-20 assessment at the baseline visit, MFM-20 scores will be derived from the post-baseline MFM-32 assessments performed by the patient, and analyses will be performed on this derived data. If MFM-32 is performed at baseline but MFM-20 is performed at one or more post-baseline visits, these assessments will be set to missing and only MFM-32 scores will be summarized. The assessment will be classified as MFM-32 if any item that is unique to the MFM-32 is reported, otherwise the assessment will be classified as MFM-20.

The MFM D1+D2 score is expressed as a percentage of the maximum possible score:

$$\text{MFM-32 D1+D2 score (\%)} = (\sum \text{MFM-32 D1 items scores} + \sum \text{MFM-32 D2 items scores}) * 100 / 75$$

$$\text{MFM-20 D1+D2 score (\%)} = (\sum \text{MFM-20 D1 items scores} + \sum \text{MFM-20 D2 items scores}) * 100 / 48$$

The change from baseline in the MFM D1+D2 score and the absolute value at each time-point will be summarized for the ITT population using descriptive statistics. Mean changes in the MFM D1+D2 score and corresponding 95% confidence intervals (CIs) over time will also be presented graphically. Summaries will be presented overall and by the treatment received in the previous Trophos study. Patients who only participated in study TRO19622CLEQ1115-1 and those who participated in study TRO19622CLEQ1275-1 will be summarized separately.

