Descriptive statistics for the actual values and change from baseline values in the MFM D1+D2 score will be presented. The results will be presented according to the timings of the MFM assessment visits in the ITT population: 26, 52, 78, 104 and every 26 weeks thereafter after baseline until the end of the study. As the MFM measurements in the natural history databases were not all collected at specific time points after baseline measurements, the measurements will be assigned to a scheduled study visit based on the time windows defined above. If more than one MFM measurement is recorded in the same time window the assessment closest to the target visit day will be used. Mean changes in the MFM D1+D2 score and corresponding 95% CIs over time will also be presented graphically.

Given sufficient data, the change from baseline in the MFM D1+D2 score at weeks 26, 52, 78 and 104 will also be analyzed using a mixed-effects model for repeated measures (MMRM). The model will include the treatment group, age, gender, SMA type, visit, treatment-by-visit interaction, and the baseline MFM D1+D2 score as covariates. Matched set will be included in the model as a random effect.

An unstructured variance-covariance matrix will be applied to model the within-patient errors. The restricted maximum likelihood method will be used for estimates of variance components. Denominator degrees of freedom will be estimated using the Kenward-Roger approximation. A treatment-by-time interaction contrast will be constructed to estimate the difference between the two groups in the mean change from baseline at each visit, and the 95% CI for the treatment difference will be reported.

If there are a sufficient number of patients in the historical comparison population for one-to-one matching to be performed, but the covariate balance between the treated and untreated groups after matching is worse than the balance before matching, then the optimal full matching described in Section 4.1.4 will be performed, and the covariate balance in this new population will be assessed. If the covariate balance between the treated and untreated groups after optimal full matching is worse than the balance before matching (and worse than the balance after one-to-one matching, if applicable), descriptive statistics for the MFM D1+D2 score will be presented for the historical comparison population, and the treatment effect in the pooled ITT and historical

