4.4.3.2 MFM Responders

Responder rates, where a responder is defined as no worsening from baseline in the MFM D1+D2 score, will be summarized at each time-point. The following assumptions will be made in the calculation of responder rates:

- Patients without an MFM assessment at a visit will be classified as non-responders. If a patient performs the MFM-20 instead of the MFM-32 at any post-baseline visit the assessment will be set to missing.
- Missing individual items will be imputed to zero.
- Patients who withdraw prematurely (for any reason) will be classified as non-responders.
- Patients who die during the study will be classified as non-responders.

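### The ITT MFM D1+D2 curve is an observed-case mean at each visit, so if faster decliners leave more often it understates decline: little at Week 52, increasingly after Week 104

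*SAP*

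**What the plan says.** SAP 4.4.1 names MFM D1+D2 as the primary efficacy measure. Alongside change from baseline, "the absolute value at each time-point will be summarized for the ITT population using descriptive statistics". It adds: "Mean changes in the MFM D1+D2 score and corresponding 95% confidence intervals (CIs) over time will also be presented graphically". The missing-data rule in SAP 4.4.1.1 is "All observed assessments will be included in the analyses. No imputation for missing MFM scores will be performed". Scores after death are set to missing, and Protocol 4.5.1 does not replace patients who withdraw. The visit windows in SAP 4.4 are listed to Week 208 and continue. SAP 4.4.2.1 treats the MFM total score in the same way.

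Other provisions that bear on dropout:
- SAP 4.4 keeps early-discontinuation assessments and assigns each to a visit window.
- SAP 4.4.1.2, a repeated-measures model for the comparison with natural history, fitted only if data suffice: "the change from baseline in the MFM D1+D2 score at weeks 26, 52, 78 and 104 will also be analyzed using a mixed-effects model".
- SAP 4.4.3.2, for the exploratory responder rate: "Patients who withdraw prematurely (for any reason) will be classified as non-responders".
- SAP 4.4.4 is a sensitivity analysis for surgery and fracture. It sets further scores to missing.
- SAP 4.2.3 summarizes withdrawals and their reasons.
- Protocol 6.12 plans a disease-progression model, reported outside the clinical study report.
- Protocol 6.7 requires the MFM summaries by the dose taken at the assessment.

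**The concern.** In a progressive disease, a patient who declines and then withdraws or dies drops out of every later mean, and the earlier loss is not carried forward. If such patients leave more often than others, the mean of those remaining drifts upward relative to the whole cohort. The plotted CI reflects sampling error among those remaining, not this selection.

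This matters because Protocol 1.2.4 already reads a within-group result from this study as sustained motor function, and long-term effectiveness is a stated purpose. The selection effect accumulates with follow-up. After Week 104 the SAP has no model-based estimate of MFM change at all.

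**Working it through.** **1. What can be reproduced.** The plan states no dropout rate and no precision or power for this curve, so it has no figure of its own to reproduce. One reported result can be checked, because its SD is used in step 5. Protocol 1.2.2 gives a 24-month effect of 2.0 (96% CI -0.25 to 4.25), p=0.0676.
- SE = 2.25/2.054 = 1.096; z = 2.0/1.096 = 1.826; two-sided p = 0.068. This agrees.
- Arm sizes follow from the serious adverse event percentages: 34/0.315 = 108 and 29/0.509 = 57.
- SD of 24-month change = 1.096/√(1/108 + 1/57) = 6.69 (an unadjusted approximation).

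**2. Identity.** Let d be the fraction gone, S the mean change of those still seen and L the mean change of those gone. The full-cohort mean is (1-d)S + dL, so the observed-case error is S minus that, which equals d(S-L). With d = 20% and a gap of 3 points it is 0.6; with 20% and 6 points, 1.2; with 30% and 6 points, 1.8.

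**3. Simulation, assumption set A.** From the documents: mean slope -1.05 points/year (the placebo progression rate in Protocol 3.3.1) and 26-weekly visits to Week 208. Assumed: n=130 (the SAP ceiling is 170; n does not drive the bias), slope SD 1.5/year, residual SD 2.2 with a shared baseline error, and withdrawal at each visit logistic with intercept -3.2 plus 0, 0.1 or 0.2 per point of prior decline. The odds ratios per point are exp(0.1) = 1.11 and exp(0.2) = 1.22.

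| | Week 52 | Week 104 | Week 156 | Week 208 |
|---|---|---|---|---|
| True mean | -1.05 | -2.10 | -3.15 | -4.20 |
| Observed case, +11% per point | -1.02 | -1.97 | -2.78 | -3.37 |
| Bias | 0.03 | 0.13 | 0.37 | 0.83 |
| Observed case, +22% per point | -0.99 | -1.78 | -2.18 | -2.09 |
| Bias | 0.06 | 0.32 | 0.97 | 2.11 |

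Retention at Week 208 is 69% and 59% respectively. With no link between dropout and decline there is no bias.

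**4. Early-discontinuation scores.** Suppose every leaver supplies one score in the window of departure. In a repeat run of the 22% setting, Week 156 moves from -2.19 to -2.50 and Week 208 from -2.07 to -2.58. The bias falls from 0.96 to 0.65 (32% removed) and from 2.13 to 1.62 (24% removed).

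**5. Sensitivity to spread, assumption set B.** Set A implies a 24-month SD of √((2×1.5)² + 2×2.2²) = √18.68 = 4.3, against 6.69 from step 1. Set B uses 6.69, with 75% of that variance from slopes, 20% dropout by Week 104 and odds of leaving doubled per SD of worse decline. At -1.05/year the observed means at Weeks 52, 104, 156 and 208 are -0.92, -1.42, -1.48 and -1.18. At -2/year (Protocol 1.2.4 reports more than 2 points/year off drug) they are -1.86, -3.31, -4.34 and -4.97 against -2, -4, -6 and -8: flatter, but still declining. Over all the informative-dropout scenarios tried, which reach 30% dropout and tripled odds, the bias is 0 to 0.36 at Week 52 and 0.33 to 1.74 at Week 104.

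**6. Would a model help?** In set A, an unstructured likelihood fit is within 0.06 points of the truth. In set B at Week 104 it returns -2.10 (true -2.10; observed case -1.42) when dropout follows the last observed change. When dropout follows the unobserved slope it returns -1.72 (observed case -1.31), which removes about half the bias.

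**The case against.** The strongest reply has five parts.

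*Efficacy is descriptive.* The primary objective is safety, and SAP 4.4 says "As this is a single arm, open-label study no formal hypothesis testing will be performed". True, and this limits the weight of the point. But a descriptive curve can still mislead.

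*The early visits are nearly unaffected.* In set A the bias at one year is at most 0.06 points. A reader might infer that the 12-month statement in Protocol 1.2.4 is an artefact of dropout. The documents do not support that: they report no dropout for that analysis, and the set A bias at that time is trivial. This stands.

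*Guards already exist.* The repeated-measures model uses all observed scores to Week 104, and the responder rate counts leavers as failures. Both help, but neither alters the ITT curve. The model estimates a contrast with natural history and stops where the bias starts to grow. The responder rate is exploratory, dropout pushes it the other way, and the SAP does not say how to read the two together.

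*The direction is unknown.* Protocol 4.3.1 permits nusinersen, so decliners need not leave to receive it. Country-specific closure and the fixed UK duration (Protocol 3.2) create missingness that is plausibly unrelated to decline. If better patients leave more often, the sign reverses. All of this stands, and it is why the point is conditional.

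*A model has its own assumptions.* Its near-perfect recovery in set A follows from simulating dropout on observed decline. This also stands, and the fix allows for it.

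**Conclusion.** The point holds in conditional form. The ITT curve for MFM D1+D2 is an observed-case mean, and nothing in the SAP corrects it for selective dropout. If dropout tracks decline, it understates decline by amounts that are negligible at Week 52 and modest at Week 104 under set A, and that can reach 0.8 to 2.1 points by Week 208. For scale, the previous trial's treatment effect was 2.0 points. The larger spread of set B gives larger values. Every size rests on assumed dropout rates and an assumed dropout-decline link. The set A figures also leave out early-discontinuation scores, which would remove roughly a quarter to a third of the late bias in the stronger setting if all leavers attended.

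A reader might go further and infer that the curve will show a false plateau that passes for maintained function. The documents do not support this. In set A a flat late segment needs the stronger setting. Even there it lies about 2 points below baseline, whereas SAP 4.4.3.2 defines response as no worsening from baseline. This is a worthwhile, inexpensive improvement to the late-visit analysis, not a flaw that invalidates the plan.

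**What to change.** In SAP 4.4.1, keep the observed-case table and graph and add beside them the repeated-measures model of SAP 4.4.1.2, fitted to the ITT population without the treatment terms (including treatment-by-visit) and the matched-set term. Its terms are visit, baseline D1+D2, age, gender and SMA type, with unstructured covariance, over all visits with adequate data. Report adjusted mean change and 95% CI per visit, and do the same for the MFM total score.

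Also:
- show per visit the number assessed, cumulative withdrawals and deaths, and the last observed change of leavers;
- add a delta-adjusted or pattern-mixture sensitivity analysis, since the model removes only part of the bias when dropout follows unobserved decline;
- keep the summaries by dose at assessment required by Protocol 6.7. The model spans both dosing periods and must not replace them.

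The cost is SAP wording and a few outputs, with no new data and no hypothesis test. The downsides are that the model assumes missing scores are predictable from observed ones, and that it projects scores past death, so deaths must be shown beside it. The late-visit figures may also be less favourable.

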4.4.1.2 Comparison with Natural History Data

Once the matched samples have been obtained, the covariate balance between the ITT and historical comparison populations, and between the treated and untreated groups in the matched patient population will be assessed (for age, gender, SMA type and baseline MFM D1+D2 score). Standardized mean differences and the ratio of the variances in the treated and untreated groups will be compared for each variable before and after matching. Medians, interquartile ranges (IQR) and ranges will also be compared for continuous variables.

If weights will be used in the analysis due to optimal full matching, they will also be used in calculating the balance measures. Each matched treated unit will receive a weight equal to one. Each matched untreated unit will receive a weight proportional to the number of treated units in its matched set divided by the number of untreated units in the set. For example, if a matched set contains one untreated unit and k treated units, the untreated unit would receive a weight proportional to $k/1=k$. The weights of the untreated units are scaled so that the sum of the weights is equal to the number of unique matched untreated units. Thus each matched untreated unit will receive a weight equal to $T_S/U_S / (T_N/U_N)$, where T_N and U_N are the total number of unique matched treated and untreated units, respectively, and T_S and U_S are the respective number of matched treated and untreated units in each matched set.

For a continuous variable the standardized mean difference, d , is defined as:

$$d = (x_t - x_u) / \sqrt{[(s_t^2 + s_u^2) / 2]}$$

where x_t and x_u denote the sample mean in the treated and untreated groups, respectively, and s_t^2 and s_u^2 denote the respective sample variances. For a binary variable the standardized mean difference is defined as:

$$d = (p_t - p_u) / \sqrt{[(p_t(1 - p_t) + p_u(1 - p_u)) / 2]}$$

where p_t and p_u denote the proportion of the binary variable in the treated and untreated groups, respectively (Austin 2009).

If the balance achieved between the two groups after matching is better than the covariate balance before matching, descriptive statistics for the MFM D1+D2 score will be presented for the matched patient population and the treatment effect will be estimated. An absolute standardized mean difference < 0.25 and a variance ratio of 0.5 to 2 for each variable indicate an acceptable balance between the two groups.

Descriptive statistics for the actual values and change from baseline values in the MFM D1+D2 score will be presented. The results will be presented according to the timings of the MFM assessment visits in the ITT population: 26, 52, 78, 104 and every 26 weeks thereafter after baseline until the end of the study. As the MFM measurements in the natural history databases were not all collected at specific time points after baseline measurements, the measurements will be assigned to a scheduled study visit based on the time windows defined above. If more than one MFM measurement is recorded in the same time window the assessment closest to the target visit day will be used. Mean changes in the MFM D1+D2 score and corresponding 95% CIs over time will also be presented graphically.

Given sufficient data, the change from baseline in the MFM D1+D2 score at weeks 26, 52, 78 and 104 will also be analyzed using a mixed-effects model for repeated measures (MMRM). The model will include the treatment group, age, gender, SMA type, visit, treatment-by-visit interaction, and the baseline MFM D1+D2 score as covariates. Matched set will be included in the model as a random effect.

An unstructured variance-covariance matrix will be applied to model the within-patient errors. The restricted maximum likelihood method will be used for estimates of variance components. Denominator degrees of freedom will be estimated using the Kenward-Roger approximation. A treatment-by-time interaction contrast will be constructed to estimate the difference between the two groups in the mean change from baseline at each visit, and the 95% CI for the treatment difference will be reported.

If there are a sufficient number of patients in the historical comparison population for one-to-one matching to be performed, but the covariate balance between the treated and untreated groups after matching is worse than the balance before matching, then the optimal full matching described in Section 4.1.4 will be performed, and the covariate balance in this new population will be assessed. If the covariate balance between the treated and untreated groups after optimal full matching is worse than the balance before matching (and worse than the balance after one-to-one matching, if applicable), descriptive statistics for the MFM D1+D2 score will be presented for the historical comparison population, and the treatment effect in the pooled ITT and historical

comparison populations will be estimated using the MMRM model described above, but without the matched set random effect.

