The PK and efficacy data from Study TRO19622CLEQ1275-1 were used to investigate the relationship between olesoxime PK exposure (i.e., average trough concentration [ $C_{average}$ ]) and the primary efficacy outcome (i.e., MFM D1 + D2 score). The results of this analysis indicated that the effect of olesoxime did not reach a plateau at the dose of 10 mg/kg QD and that higher doses may lead to an increase in efficacy (see PK/pharmacodynamic [PD] report) (see Section 3.3.1).

Baseline samples from 119 patients previously enrolled in Study TRO19622CLEQ1275-1 (81 patients in olesoxime arm and 38 patients in placebo arm) were analyzed. All patients previously on olesoxime in Study TRO19622CLEQ1275-1 had detectable predose olesoxime concentrations at baseline of Study BN29854. Olesoxime concentrations ranged from 23 to 801 ng/mL, corresponding to 0.3% to 9.5% of  $C_{average}$  observed in Study TRO19622CLEQ1275-1. The time after last dose from Study TRO19622CLEQ1275-1 was 2.4–4.0 years. Olesoxime was not detected in the OLEOS baseline samples from any of the 38 patients previously randomized to placebo arm in Study TRO19622CLEQ1275-1. Roche currently assumes that these residual concentrations are secondary to the accumulation of olesoxime, a cholesterol derivative, in a deep compartment.

Based on currently available data, residual exposure to olesoxime for periods up to 6 years does not appear to be associated with any newly emerging safety risks.

Study TRO19622CLEQ1275-1 indicated that treatment with olesoxime maintained motor function in SMA Type 2 and non-ambulatory Type 3 patients, as measured by the MFM, and decreased disease-related complications.

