4.1.4 Matched Patient Population

In order to account for differences between patients in the ITT population (treated) and those in the historical comparison population (untreated), several matching methods for

balancing baseline covariates will be considered depending on sample size, data availability and data quality.

If there is sufficient data, each individual in the ITT population will be matched to an individual in the historical comparison population (one-to-one matching) with respect to age, gender, SMA type and baseline MFM D1+D2 score. Gender and SMA type will be matched exactly, followed by optimal Mahalanobis distance matching within these groups for the age and baseline MFM D1+D2 score. In order to determine the 'closeness' between individuals to use in matching, we define the Mahalanobis distance, D_{ij} , between the i^{th} treated unit and j^{th} potential untreated unit:

$$D_{ij} = (x_i - x_j)^T \Sigma^{-1} (x_i - x_j)$$

where x_i and x_j are the observed values of the matching variables (age and baseline MFM D1+D2 score) for treated unit i and untreated unit j , respectively, and Σ is the variance covariance matrix of X in the untreated group. Optimal matching will be used to minimize the total distance $T = \sum D_{ij}$.

Patients in the ITT population who erroneously perform the MFM-20 assessment at the baseline visit will not be included in the matched patient population. MFM-20 assessments performed at any post-baseline visit will be set to missing.

If one-to-one matching does not produce enough matches (if > 10% of the ITT population is not matched), optimal full matching will be performed, where one untreated unit may be matched to more than one treated unit, but each treated unit will only be matched to one untreated unit. The maximum number of times each untreated unit is matched with a treated unit will be equal to the smallest integer value greater than or equal to the maximum ratio of treated to untreated units in each combination of gender and SMA type (Type 2 male, Type 2 female, Type 3 male and Type 3 female). The number of times each untreated unit is matched will be monitored to ensure that the treatment effect estimate is not based on only a small number of untreated units.

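### The SAP accepts a matched natural-history sample if balance is merely better than before, so its own balance limits decide nothing

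*SAP*

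**What the plan says.** SAP 4.1.4 matches each ITT patient to one untreated patient: "Gender and SMA type will be matched exactly, followed by optimal Mahalanobis distance matching within these groups" for age and baseline MFM D1+D2. No caliper is stated. It gives one count-based reason to change method: "If one-to-one matching does not produce enough matches (if > 10% of the ITT population is not matched), optimal full matching will be performed". Under full matching, an untreated patient may be reused up to the ceiling of the largest treated-to-untreated ratio across the four gender-by-type strata.

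SAP 4.4.1.2 gives the balance rules:

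- Matched descriptives are presented and the treatment effect is estimated "If the balance achieved between the two groups after matching is better than the covariate balance before matching".
- The following sentence sets limits: "An absolute standardized mean difference < 0.25 and a variance ratio of 0.5 to 2 for each variable indicate an acceptable balance" between the groups. It names no consequence if they are missed.
- Where one-to-one matching was feasible but "the covariate balance between the treated and untreated groups after matching is worse than the balance before matching, then the optimal full matching" of 4.1.4 is performed.
- Matching is abandoned for the pooled, unmatched populations if full matching leaves balance "worse than the balance before matching (and worse than the balance after one-to-one matching, if applicable").

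The matched descriptives and graphs run every 26 weeks to the end of the study. The MMRM covers weeks 26, 52, 78 and 104, given sufficient data, with age, gender, SMA type and baseline MFM D1+D2 as covariates.

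**The concern.** Every balance decision compares the matched sample with the unmatched one. None compares it with the limits the SAP itself calls acceptable. A poor starting point is easy to improve on, so a match can pass while still failing the plan's own standard.

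The words better and worse are also undefined. Four covariates are assessed on two measures each. If age improves and baseline MFM D1+D2 deteriorates, no rule says which branch applies, and the analyst would choose after seeing the data of an open-label study.

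A secondary objective of the study is effectiveness relative to natural history on the MFM, and the MFM total score follows the same procedure. Protocol 1.2.2 says that patients aged 6 to 15 are more likely to worsen substantially. Residual age imbalance is therefore prognostic and enters the matched means and graphs without adjustment.

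**Working it through.** The plan gives no figure to reproduce here. The check has three parts.

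**1. Tracing the branches**

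| Decision | Test used | Uses 0.25 or 0.5 to 2? |
|---|---|---|
| Accept the matched sample | balance better than before | no |
| One-to-one to full matching | more than 10% of ITT unmatched | no |
| One-to-one to full matching | balance worse than before | no |
| Abandon matching | full matching worse than before, and worse than one-to-one if applicable | no |

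Example: at most 10% are unmatched and the baseline MFM standardized mean difference (SMD) moves from 0.80 to 0.38, with the other covariates no worse. That is better, so the match is accepted and full matching is not run, although 0.38 exceeds 0.25. Gender and SMA type are matched exactly, so only age and baseline MFM D1+D2 can breach the limits.

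**2. How often this could happen**

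The documents give neither the size of the control pool nor the covariate shift, so these are assumptions:

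- 119 treated patients. This borrows a count from Protocol 1.2.2 ("Baseline samples from 119 patients previously enrolled in Study TRO19622CLEQ1275-1"); it is not a stated ITT size.
- Strata of 35/35/15/15%.
- Normal covariates, with the same standardized shift on age and baseline MFM.
- Optimal one-to-one Mahalanobis matching within strata, without a caliper.
- Better means a smaller absolute SMD on both covariates.
- 400 runs per cell.

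SMD = |mean difference| / √[(s_t² + s_u²)/2], as in the SAP. Each cell gives the mean SMD after matching, then the share of runs accepted (better, at most 10% unmatched) while outside the limits.

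| Controls per treated | Shift 0.3 | Shift 0.5 | Shift 0.8 |
|---|---|---|---|
| 1.0 | 0.21; 36% | 0.38; 59% | 0.68; 65% |
| 1.25 | 0.18; 35% | 0.34; 92% | 0.61; 97% |
| 1.5 | 0.13; 12% | 0.27; 78% | 0.52; 100% |
| 2 | 0.09; 1% | 0.17; 20% | 0.38; 98% |
| 3 | 0.05; 0% | 0.10; 0% | 0.24; 58% |

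At 1.0 the shares are held down because the 10% rule fires in 34% to 37% of runs. From 1.25 upward it fires in 3% or fewer.

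**3. Whether full matching as written would help**

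The cap is the ceiling of the largest treated/untreated ratio over strata. With 1.2 controls per treated patient in every stratum, 1/1.2 = 0.83 and the cap is 1. With 1.5, 1/1.5 = 0.67 and the cap is again 1. With a cap of 1 and no caliper, full matching is the same optimal assignment as one-to-one.

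A second simulation confirms this: 120 treated, 200 runs, assumed 0.6 SD shift on one covariate, equal stratum shares in both groups. The table shows the mean of the largest SMD.

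| Controls per treated | One-to-one | Full matching, SAP cap | Up to two uses |
|---|---|---|---|
| 1.2 | 0.41 | 0.41 | about 0.16 |
| 1.35 | 0.34 | 0.34 | about 0.14 |
| 1.5 | 0.28 | 0.28 | about 0.13 |

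If stratum shares vary at random, some strata run short and the cap sometimes rises to 2 or more. The SAP's full matching then averages 0.28, 0.31 and 0.28, still above 0.25.

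**The case against.** The strongest reply is that the modelled effect is already protected. The between-group estimate with its 95% interval comes from an MMRM that adjusts for age and baseline MFM D1+D2, so an SMD of 0.4 does not pass unaltered into that estimate. This stands, and it confines the concern mainly to the matched descriptives. It is not a full answer: the MMRM stops at week 104 and depends on sufficient data, while the unadjusted means and graphs continue.

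A breach would also be visible, because the SAP compares SMDs, variance ratios, medians and ranges before and after matching. Controls are preselected to resemble the ITT population in age and SMA type, no hypothesis is tested, and the primary objective is safety. All of this limits the weight of the point. None of it says what happens when a breach is seen.

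Three stronger readings are tempting, and the documents do not support them:

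- That this is the only comparative efficacy analysis. SAP 4.4.2.4 also compares SMA-related complications with the NatHis-SMA population.
- That full matching will never be tried. The 10% rule can trigger it, though that rule counts matches and ignores their quality.
- That the full matching already in SAP 4.1.4 would cure the imbalance. With its present cap it often returns the same match. The gain in the last column of the second simulation belongs to a method the SAP does not specify.

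**Conclusion.** The gap in the rules is certain: no branch uses the stated limits, and better is undefined when covariates move in opposite directions. The plan can therefore accept a match that it would itself call unacceptable on age or baseline MFM D1+D2.

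The practical size is uncertain. The share of one-to-one matches accepted outside the limits ranges from 0% to 100% over the assumed pool sizes and shifts. It is 0% with three controls per treated patient and a shift of 0.3 or 0.5, and 97% or more with 1.25 to 2 controls and a shift of 0.8. The point is worth correcting before the matching is run, chiefly for the matched means and graphs. It does not show that the adjusted estimate is materially biased.

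**What to change.** Amend SAP 4.1.4 and 4.4.1.2 as follows:

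1. Accept a match only if all four covariates have an absolute SMD below 0.25 and a variance ratio of 0.5 to 2. This replaces the better and worse tests and settles mixed results.
2. If one-to-one matching fails, run full matching with the reuse cap set to at least 2, and apply the same limits.
3. Use the match with the smallest maximum absolute SMD.
4. If neither match meets the limits, label the matched descriptives and graphs as not acceptably balanced, and report the covariate-adjusted MMRM as the comparison. State in advance whether it is fitted to the matched sample or to the pooled populations.

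The cost is SAP wording and one more matching run. Reusing controls widens the interval somewhat: at the extreme, with every selected control used twice, 119 treated patients would rest on about 60 distinct controls (119/2 = 59.5). The SAP already plans to monitor how often each control is used.
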